6.4 Template for Describing Each Project Intervention

Each NEYAI project is delivering a unique intervention. It is important therefore to have a clear description of that intervention for the evaluation since, where an intervention is shown to be effective, this will be valuable in helping to explain why this may have happened; additionally, it may also help to guide those who wish to replicate the intervention elsewhere. The interventions in the evaluation, as listed in Table 1 above, were selected to represent each project's most *substantial and sustained* intervention and, in that sense, could be regarded as the 'flag-ship' of each project, the impact of which will determine the success of their entire project.

A template will be prepared by the evaluation team to enable each project to prepare a detailed description of its intervention using the following headings:

⁹⁷ This is an important assumption though seldom acknowledged due to the tendency to treat the 'personal' and the 'professional' as separate and unrelated domains of staff capacity. It is significant therefore that a recent review of the early childhood education drew attention to how child development is influenced by the capacities of all adults who interact with the child on a regular basis, both parents as well as childcare staff: '... although the call for more effective strategies to build parenting capacities is broadly accepted, the unmet, skill-building needs of service providers in these domains are acknowledged less frequently. Although many preschools are staffed by highly trained professionals, a large proportion of staff in early care and education programs have limited education, constrained work experience, and high rates of depression. Thus, large numbers of vulnerable children and highly stressed staff are engaged in dysregulated interactions on a daily basis that compromise early learning and undermine the ability to manage routine challenges and normative life stresses. Other indicators of unmet staff training needs include complaints about high rates of problematic child behaviors, increasing antipsychotic drug prescriptions for children as young as age 3, and large numbers of children being expelled from preschool programs. These signs of impending staff burnout underscore the need for expanded professional development activities to strengthen emotional health and executive function skills and self-regulation capacities of early childhood service providers.' (Shonkoff, 2011:983)

- ✓ Name of project and intervention
- ✓ Logic model of intervention and how it is expected to work in order to produce outcomes, including the mediating role of staff capacity
- ✓ History of intervention including evidence of its effectiveness in Ireland and elsewhere
- ✓ Target group of intervention (children, parents, staff) including measures used to recruit, retain and minimise drop-out
- ✓ Description of the intervention including method used to deliver the intervention such as individual-work or group-work, home-based or centre-based, etc.
- ✓ Duration of intervention broken down by number and length of each session including whether homework is part of the programme
- ✓ Resources needed to deliver the intervention such as manual, videos, handouts, etc.
- ✓ Staff recruitment, training and skills required to implement the intervention
- ✓ Organisational structures to support intervention at childcare centre-level, project-level, inter-agency level
- ✓ Breakdown of the cost of undertaking the intervention, focusing on the additional cost over and above the existing 'overhead' cost of the centre and its staff
- ✓ Challenges encountered during implementation and how these were addressed.

The information provided by each project will form the basis for preparing case studies of effective interventions where the evaluation has already shown evidence of a significant impact on parent, child or staff outcomes. This information will also act as a 'manual' for other projects wishing to implement the intervention.

6.5 Extraction of Data on Area Characteristics

Data will be extracted on the area characteristics of each childcare centre participating in the evaluation, aggregated to project-level, using the summary Pobal-Haase Index. This data is based on the Census of Population and is disaggregated at the level of Small Areas which have a minimum of 65 households and average of 100 households.

This data will serve three purposes. First, it will describe the areas being served by the childcare centres in the NEYAI and situate those 'treatment areas' in terms of their level of deprivation relative to the surrounding county and Ireland. Second, as already explained (Section 5.2), it will facilitate the selection of 'comparison areas' that match the treatment areas as closely as possible. Third, it will enable an assessment of the 'fit' between the children and parents using the childcare centres and those living in the wider catchment area; this will be done by combining data from the Parent Questionnaire and the CSO data.

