13 For that reason, the proper use of a logic model requires awareness of its limitations since 'the logic model is a model – not reality. It depicts assumed causal connections not true cause-effect relationships' (Taylor-Powell & Henert, 2008). Limitations of logic modelling include the following: (i) a logic model represents intention, it is not reality; (ii) it focuses on expected outcomes so people may overlook unintended outcomes (positive and negative); (iii) it focuses on positive change – change isn't always positive; (iv) it may simplify the complex nature of causal attribution where many factors influence process and outcomes; (v) it doesn't address whether we are doing the right thing – we may get caught up in creating a logic model and lose track of whether the program is the right thing to do; and (vi) may stifle creativity and spontaneity. (Ibid).

The left-hand side of the logic model depicts the inputs of NEYAI and are constituted by the 11 project interventions. These include both the actual services delivered to children and their parents as well as the training and mentoring of staff to deliver those services. These inputs will vary by type, duration and intensity but will also vary in the manner of their implementation. The context of each project, particularly the focus on children living in disadvantaged areas, can also be regarded as an 'input' in the sense that the uptake and effectiveness of each intervention is likely to be affected by characteristics of the target group and the target area. In this sense, context provides important information about how NEYAI is targeted, who participates, and how it influences outcomes directly and indirectly for parents and children (see Section 6.5 below).

The right-hand side of the logic model depicts the outcomes which are conceptualised as improved well-being for children and their parents. For children, this takes the form of improved physical, emotional, social and cognitive development. For parents, it includes improved individual well-being, both physical and mental, as well as improved parenting and family relationships but may also include an improved sense of social support.

Figure 1 Logic Model of National Early Years Access Initiative

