4.1 Challenges in the Research Design

NEYAI could be described as multi-faceted in that it is *multi-programme* (11 different interventions), *multi-theme* (covering different aspects of child and parent well-being using a range of new and existing programmes), *multi-site* (each project works with different childcare centres), *multi-agency* (each project comprises a lead organisation and at least two other organisations), and *multi-level*

41 These outcomes include improved understanding each other's role, greater willingness to share information, reduction in duplication, better connection to local communities, etc. See Stratham, 2011; Barlow and Scott, 2010; CfBT Education Trust, 2010; Duggan and Corrigan, 2009; Oliver, Mooney and Stratham, 2010; Robinson, Atkinson and Downing, 2008.

42 See, for example, Inquiry Team in Roscommon Child Care Case, 2010; Lord Laming, 2003.

(initiative-level, thematic-level, project-level, learning community-level). Unlike a standard 'programme' evaluation – where programme is understood as a defined set of inputs and processes, often manualised, and delivered to either a population or specific target group – each of the 11 NEYAI projects has its own unique programme. In that sense, this could be described an evaluation of 11 programmes rather than one programme.

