5.2 Comparison Group Sample

The comparison group sample is created in three stages. First, the catchment areas of the treatment group are identified in terms of demographic and socio-economic characteristics. For each NEYAI project, its catchment area is defined as the sum of the catchment areas of each childcare centre participating in the evaluation.

The data used to define these catchment areas is derived from the 2006 Census of Population, based on 'Small Areas' which have a minimum of 65 households and an average of 100 households; as such the data is almost 'street-level' and allows catchment areas to be defined precisely. This data will be expressed in terms of its deprivation score using the Pobal-Haase Index⁷². This data has the advantage that it is immediately available and, more to the point, the only data that allows areas to be defined in this way. The disadvantage is that while it is possible to match treatment and comparison areas in terms of deprivation scores, it is not possible to match them on other family characteristics which may be more relevant to this evaluation such as child and parent well-being, family functioning, neighbourhood and community factors. Nevertheless, the use of deprivation scores is the best available option and there are precedents for drawing comparison groups in this way, a notable example being the Sure Start evaluation⁷³.

Second, having established the level of deprivation in these catchment areas, a set of comparison areas will be identified which are matched as closely as possible to the treatment areas. In each of these comparison areas, childcare centres will be drawn from the Pobal database to match the

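### Deprivation is extracted by centre but aggregated to one score per project, so within the treatment group, and as a modifier of each intervention's effect, area cannot be separated from project

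*Protocol*

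**What the plan says.** Protocol Section 6.5 extracts data on the "area characteristics of each childcare centre participating in the evaluation, aggregated to project-level, using the summary Pobal-Haase Index". The source is finer than this: it "is disaggregated at the level of Small Areas", which average 100 households, and Section 5.2 values it because it "allows catchment areas to be defined precisely". Section 5.2 works at the same coarse level when it describes a project: "its catchment area is defined as the sum of the catchment areas of each childcare centre participating in the evaluation".

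Section 6.5 lists three uses for the index: describing the treatment areas, selecting comparison areas, and checking how far centre users resemble the wider catchment. Section 3 (Logic Model of Programme) expects more. It says "the uptake and effectiveness of each intervention is likely to be affected by characteristics of the target group and the target area", and it refers the reader to Section 6.5 for how context influences outcomes, directly and indirectly.

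Section 4.1 states that "each of the 11 NEYAI projects has its own unique programme". Question (ii) in Section 4 asks for whom, in which projects and through which type of intervention any impact arises. Sections 4.3 and 9.1.1 rest the impact estimate on statistical control of all measured differences between the groups.

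**The concern.** One score per project, with one programme per project, ties deprivation exactly to the intervention among the treated. If a project in a poorer area shows a smaller net impact, the data cannot say whether the area or the programme explains it. That is the question Section 3 raises.

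The second consequence concerns adjustment. Comparison areas are chosen to match the treatment areas on this index. Once it is aggregated, it can adjust only for differences between whole project areas, and the matching is meant to have removed most of those. Differences between the streets that individual centres serve remain after area matching, and a project-level score cannot show them.

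The choice also sits oddly with Section 5.1, which tests staff capacity at individual, centre and project level. Area context receives only the coarsest of these, and no reason is given.

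**Working it through.** **Inputs.** 11 projects, each with its own programme (Section 4.1); 35 children per project in each group (Section 5); one index value per project (Section 6.5). The plan's sample figures reproduce: 35 × 11 = 385 per group and 2 × 385 = 770 in all.

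**Identifiability.** Let P_p be the indicator for project p, T = ΣP_p the treatment indicator, and D the deprivation score. If each project has a single score d_p, then among the treated D = Σ d_p P_p. Likewise D × T = Σ d_p P_p over the whole sample. Both are exact linear combinations of the project indicators. The rank of each design matrix was checked numerically. Scores were simulated, since rank does not depend on their size. Three centres per project were assumed, and the results were the same for 9, 10 and 11 comparison clusters.

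| Model | Project-level score: columns, rank | Centre-level score: columns, rank |
|---|---|---|
| Treated only: 11 P_p, D | 12, 11 | 12, 12 |
| Both groups: intercept, 11 P_p, D | 13, 13 | 13, 13 |
| Both groups: intercept, 11 P_p, D, D × T | 14, 13 | 14, 14 |
| Both groups, pooled: intercept, T, D, D × T | 4, 4 | not run |

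- Row 1: among the treated, project-level deprivation is not separable from project.
- Row 2: adding the comparison group makes a main effect estimable. Each treated project's own indicator absorbs its score, so the slope comes only from the comparison clusters and must be assumed equal in both groups.
- Row 3: modification of the effect by area is not identifiable alongside separate project effects. It becomes identifiable, as one common slope, with centre-level scores that differ within projects.
- Row 4: a pooled interaction is estimable, but it rests on 11 treated clusters and assumes that the programmes do not otherwise differ.

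**Power for moderation.** Suppose k units (projects or centres) share 385 children per group, so m = 385/k. With outcome SD 1, each unit's estimated effect has sampling variance 2/m. If true effects vary between units with SD τ, a true correlation r with deprivation is observed as r × √[τ²/(τ² + 2/m)]. Power is about Φ(atanh(r_obs) × √(k − 3) − 1.96), plus a very small other tail.

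With r = 0.5 and τ = 0.2 (assumed):

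- k = 11: m = 35 and 2/m = 0.057. The ratio is 0.04/0.097 = 0.41, so r_obs = 0.32. Then atanh(0.32) × √8 = 0.94, and power is about 16%.
- k = 33: m = 11.7 and 2/m = 0.171. The ratio is 0.04/0.211 = 0.19, so r_obs = 0.22. Then atanh(0.22) × √30 = 1.21, and power is about 23%.
- k = 66: m = 5.8 and 2/m = 0.343. The ratio is 0.04/0.383 = 0.10, so r_obs = 0.16. Then atanh(0.16) × √63 = 1.29, and power is about 25%.

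At r = 0.3 with the same τ, power is 9% for 11 units and 11% to 12% for 33 to 66. At r = 0.5 with τ = 0.3, it is 21% and 38% to 45%. The values 33 and 66 assume 3 and 6 centres per project. Correlation between centres in the same project, or attrition, would lower the figures further.

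**The case against.** The strongest reply is that Section 6.5 plans no area-effect analysis. Its three uses are descriptive or concern selection, and a project aggregate suits the choice of comparison areas. The expectation of more comes from general prose in Section 3, and which covariates enter the model may be settled in an analysis plan that is not at hand. Section 6.5 also does not say that centre values will be deleted. All this is fair. What remains is that Section 3 sends the reader to Section 6.5 for how context acts on outcomes, and the level stated there cannot serve that purpose.

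The reply also points out that the Parent Questionnaire records socio-economic position (Section A) and neighbourhood conditions (Section B) for each family. These vary within projects and can serve both adjustment and the question of for whom. This stands and limits the consequence: what is lost is the area index, not all information on context.

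Three stronger readings are tempting, and the documents do not support them.

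- A reader might infer that area and intervention cannot be separated at all. The comparison areas carry deprivation scores without the programme, so a main effect is estimable under a common slope.
- A reader might infer that the pooled contrast of NEYAI with comparison is confounded by deprivation. If the matching succeeds, it is not.
- A reader might treat centre effects as known exactly and expect centre-level scores to raise power from 34% to 85–99% at a correlation of 0.5, or from 14% to 40–69% at 0.3. With the total fixed at 385 per group, more units mean fewer children in each, and sampling error removes most of that apparent gain.

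**Conclusion.** The point holds in a limited form. With the index at project level, deprivation is inseparable from project within the treatment group (12 columns, rank 11), and so is its role in modifying each intervention's effect (14 columns, rank 13). Centre-level imbalance left after area matching cannot be adjusted for with the index. The overall impact estimate is not threatened by this.

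The gain from a change is identifiability and finer adjustment, not much power: on the assumptions shown, moderation by area stays below 50% power in every case. The gain also requires projects with several centres whose deprivation differs. The protocol gives neither centre counts nor the spread within projects, and the restriction to disadvantaged areas may narrow that spread. What is restored is one common moderation slope; a separate slope for each intervention would need several centres in that project. This is a low-cost improvement of modest value.

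**What to change.** State in Section 6.5 that, in both groups, the Pobal-Haase score is kept at the level of the centre catchment in the analysis file. Link it to each child through the Centre ID that Appendix Two already records. Use it as a centre-level covariate in the impact models and as an exploratory moderator, with standard errors that recognise the centre as the unit at which it varies. Keep the project aggregate for describing areas and selecting comparison areas. Report the number of centres per project and the within-project spread of the score, so that readers can judge how much the adjustment can do.

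The cost is close to nothing. The scores are already extracted by centre, the linking identifier exists, and no address data beyond those already held are needed.

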6.6 Extraction of Data from the Growing Up in Ireland Database

Growing Up in Ireland (GUI), as already explained, is the National Longitudinal Study of Children, based on a large nationally representative sample of children and their parents. An important by-product of the GUI is the creation of a national set of benchmarks on the well-being of children and their parents, based on standardised instruments that produce consistently valid and reliable results in different settings and at different times. That is why, in designing the questionnaires for this evaluation, instruments are drawn from the GUI wherever possible. In light of that, data will be extracted from the GUI to provide 'benchmarks' for the treatment and comparison groups.

The use of GUI as benchmark data has some similarities with the way the UK's Millennium Cohort Study (MCS)⁹⁸, itself similar to GUI, was used in the national evaluation of Sure Start (NESS)⁹⁹. However there are also important differences. In the national evaluation of Sure Start, a population-based approach (or 'intention to treat design') was adopted to assess its impact in each area and involved comparing samples of children in NESS areas and matched MCS areas¹⁰⁰. This is different to the evaluation of NEYAI where we use a target-group approach (or 'per protocol design') to assess impact by comparing the treatment group with the comparison group. Nevertheless, the experience of using MCS in NESS draws attention to the need to ensure that, for each benchmark used, all comparisons are based on variables which are measured in an identical manner. The NESS experience also indicates that due consideration needs to be given to the different times when data is collected¹⁰¹ (2007/9 for GUI data, 2011/13 for NEYAI data), particularly time-sensitive events (such as the timing of immunisation for three year-olds which affected the comparability of

98 The Millennium Cohort Study (MCS) is based on around 19,000 children born in the UK in 2000/1. Four cohorts of children are being tracked at ages (i) nine months (ii) three years (iii) five years and (iv) seven years. The study is being carried out by the Centre for Longitudinal Studies (CLS), based at the Institute of Education, University of London.

99 National Evaluation of Sure Start Team, 2010.

100 'The comparison group of Millennium Cohort Study (MCS) children and their families, against which the NESS sample was compared, was selected from the entire MCS cohort. Their selection was based upon identifying and selecting children living in areas with similar economic and demographic characteristics to those in which the NESS [National Evaluation of Sure Start] sample resided, but which were not SSLP-designated areas and thus did not offer SSLP services. This enabled the NESS research team to make comparisons with children and families from areas as similar as possible to the NESS Impact Study areas to detect the potential effects of SSLPs on children and families' (National Evaluation of Sure Start Team, 2010:iv).

101 In evaluating the impact of Sure Start when children reached 5 years, the NESS team were unable to test for the possible effect that 'time of measurement' might have on the comparison of MCS data (collected between January 2006 and March 2007) and NESS data (collected between June 2007 and June 2009). As a result, the report highlights that 'time of measurement cannot be ruled out as an alternative explanation for almost any NESS/MCS differences – and thus SSLP effects – discerned. ... any and all discerned effects of SSLPs – whether positive or negative in character – potentially could be attributed to time-related changes in communities and/or the larger society that had nothing to do with SSLPs' (National Evaluation of Sure Start Team, 2010:7 and 39).

MCS and NESS areas), or different approaches to measuring each benchmark (such as self-report, interview, direct observation)¹⁰².

6.7 Monitoring Impact of Learning Community

The learning community is an innovative feature of NEYAI in the sense that it makes a specific commitment to 'learning' as an outcome to be achieved collectively by the projects. This is additional to the learning that will emerge through this evaluation although, in practice, the two processes are likely to be inter-connected. The learning community held its first meeting on 13th-14th September and has agreed to meet three times a year over the course of the initiative.

From the perspective of the evaluation, two broad outcomes of the learning community will be monitored and evaluated. The first and main outcome is learning that directly impinges on the interventions that are being evaluated. This type of learning is particularly important because it may increase the likelihood of positive impacts - for some or all projects - in the outcome areas affecting children, parents and staff. The second outcome is learning associated with other work being undertaken by the projects, though not part of the intervention that is being evaluated.

Evaluation of the learning community and its achievements will entail attendance at, and direct observation of, all meetings. At the end of each meeting, every project will be asked to complete a brief online questionnaire designed to capture the two broad outcomes of the learning community described in the previous paragraph (see Appendix Six). The data generated by this process will be used to provide an overall assessment of the learning community as well as assist in the interpretation of positive impacts that may be traceable, directly or indirectly, to the learning community. More details on how this data will be analysed is presented below (Section 9).

7. Timeframe for Data Collection

The core principle underpinning data collection for the treatment group is that baseline data must be collected before any significant intervention takes place while follow-up data must be collected as soon as possible after the end of the intervention. Applying this principle in practice requires some flexibility since the 11 projects vary in the timing of their interventions. Taking this into account, a

102 'Any effects discerned in the evaluation have to be considered "putative" because the data for the NESS and MCS samples of 5-year olds and their families were collected two years apart and by two different research teams. This makes attributing any discerned SSLP effects to SSLP exposure per se difficult, as they could potentially reflect changes taking place in communities or society more generally across the two-year period in question or be the result of differences in approaches to measurement by the two research teams, although close cooperation did occur with respect to staff training. Indeed, possible time of measurement effects were identified in the NESS Impact Study when children were 3 years old with respect to child immunisations. That is, apparently positive effects of SSLPs on immunisations were found to be possibly a function of the time difference between when NESS and MCS 3-year old data were collected rather than an effect of SSLPs on immunisations' (National Evaluation of Sure Start Team, 2010:iv).

timeframe for data collection will be agreed with each project within the parameters that all baseline data will be collected by the end of October 2012 and all follow-up data will be collected by the end of June 2013.

There are fewer constraints on data collection for the comparison group but the timeframe will broadly mirror that of the treatment group. As indicated above, further work is required, in collaboration with Pobal, to support data-collection for the comparison group, possibly through the County Childcare Committees or Partnerships or both.

8. Ethical Considerations

The main ethical and legal requirement in the study is to ensure that the right of children, parents and staff to privacy and confidentiality is respected at all times. This right is enshrined in the Data Protection Acts 1988 and 2003.

Bearing this in mind, the consent of each parent is required to allow childcare staff assess each child using the Child Questionnaire. Similarly, the consent of each parent is required before any contact details can be passed over to the evaluation team in order to carry out the interview using the Parent Questionnaire.

In order to meet these requirements, a standard Parent Consent Form has been prepared (Appendix Seven). This form explains the nature of the study and the guarantee that the parent's and child's privacy and confidentiality will be protected at all times. Parents who are randomly selected to take part in the study will be invited by staff in each childcare centre to sign the consent form.

The central mechanism in the evaluation to ensure privacy and confidentiality is the use of numerical data identifiers on all questionnaires; no names or other personal identifiers are written on any of the questionnaires. All data collection, data entry and data storage are based on these numerical data identifiers such that personal information is never collected and stored with the research data, making them anonymous. All data derived from the questionnaires is stored on password-protected computers, encrypted, and user-restricted.

9. Data Analysis

There are two parts to the data analysis. The first follows completion of baseline data collection in October 2012 and will result in an Interim Report in early 2013. The second follows completion of follow-up data collection in June 2013 and will result in a Final Report in early 2014. These two parts

of the data analysis constitute a seamless stream of work and, in that sense, the baseline data analysis might be seen as preparatory to the combined analysis of baseline and follow-up data.

Both parts of the analysis will be linked thematically around the three core themes of child well-being, parent well-being and staff capacity. Specifically the thematic analysis will focus on how these concepts are defined, determined and connected to each other. These themes also cover the three core questions in the terms of reference¹⁰³:

- ✓ how to improve outcomes for children, particularly ‘improved health / learning and school readiness’
- ✓ how to improve the well-being of parents and their capacity to nurture the child’s development through ‘parent’s skills and improved parenting support’.
- ✓ how to improve the capacity or ‘up-skilling’ of childcare staff.

The over-riding consideration in the data analysis, as in the overall evaluation, is to establish if NEYAI has an impact and, if so, how. Naturally, it cannot be known in advance if the evaluation will show a measurable impact. However, even if no measurable impact is detected – or only the slightest impact – the proposed data analysis is still capable of generating useful results because, in addition to assessing impact, the evaluation will also address questions, arguably more generic ones, about the measurement of child well-being, parent well-being and staff capacity, and the relationships of influence that may link these together. Irrespective of the impact of the initiative therefore, the evaluation is likely to produce valuable insights that could have useful policy and practice implications for the early years sector.

